RESPONSE: Functional endoscopic sinus surgery (FESS) is a commonly performed procedure in the United States to treat chronic rhinosinusitis. Common practice is to prescribe prophylactic antibiotics postoperatively. This is similar to the long tradition of prophylactic antibiotics after tonsillectomy. The American Academy of Otolaryngology - Head and Neck Surgery recently strongly recommended against prophylactic antibiotics after tonsillectomy. In this light, this study would demonstrate the lack of need for antibiotics after FESS. Currently [name] does not prescribe antibiotics except when evidence of active infection was found during surgery. [name] currently prescribes antibiotics. This study would prospectively compare the two groups in a randomized fashion. Two previous studies have been performed (Jiang et al. Postoperative antibiotic care after functional endoscopic sinus surgery. *Am J Rhinol* 22, 608-612, 2008); (Albu, et al. Prophylactic antibiotics in endoscopic sinus surgery: A short follow-up study. *Am J Rhinol* 24 306-309, 2010.) These studies were both randomized, placebo controlled prospective studies. Albu et al found that amoxicillin/clavulanate improved the outcome in the "early blood crust healing" and the endoscopic score was improved. Jiang et al. showed that amoxicillin/clavulanate did not improve short term outcomes of FESS. Both studies were limited by a lack

of a prospective instrument to evaluate symptoms. We plan to use the Sinonasal outcomes test -22 (SNOT-22), which is a validated quality of life instrument in sinusitis.

4) What is the estimated completion date? (MM/YYYY)

RESPONSE: 06/2015

5) Who specifically (name, title, and department) is going to perform the coordinator function? Discuss his/her relevant qualifications (training, education, experience):

The PI, [name], has assumed coordinator function. He has had experience and training through the Harvard Catalyst education offerings in clinical studies.

6a) Who is going to supervise the study coordinator(s)? When applicable, indicate if support and oversight will be provided by the Ophthalmology Clinical Research Office (OCRO).

6b) Describe the PI's plan to provide adequate training, and supervision (e.g., regular meetings, training opportunities):

[name] will be supervising all aspects of the study and meets regularly (weekly) with [name] on matters of enrollment, patient compliance, and monitoring of adverse events.

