7) Delegation of Significant Study-Related Tasks- If non-physicians are tasked to assess clinical response to an investigational therapy, provide medical care to subjects during the course of the study, assess inclusion/exclusion criteria, and evaluate adverse events, list their names in the table below and complete:

Name	Delegated Tasks	Qualifications- Licensing, or Certification	Training
[name] / [name], follow-up, evaluation for adverse reactions, data collection	MD	Residency and fellowship training in otolaryngology and rhinology
Pharmacy staff (supervised by [name])	Distribution of study drug	Pharm D	Doctorate in pharmacy

8) Indicate all MEE sites where research activities occur:

- Boston-MEEI [name]
- Boston Longwood Medical Area – [name]
- Boston-SERI [name]
- Braintree - [name]
- Concord - [name]
- Duxbury - [name]
- East Bridgewater - [name]

- Milton - [name]
- Newton - [name]
- Quincy - [name]
- Stoneham - [name]
- Stoneham - Retina Consultants-[name]
- Weymouth - [name]

9) Are there any non-MEE sites involved in this study? YES NO (If NO, skip to question 11)

IF YES, Is MEE the lead site or coordinating center? YES NO

10) In the table below, list each non-MEE sites where research activities will occur, and the status of IRB review at each site (indicate if the intent is for MEE to serve as the IRB of record for all study sites (cede review) or if IRB review will be required at other sites:

Non-MEE Sites	IRB Review Status (i.e., review pending, approved, seeking cede review)

SUBJECT INFORMATION

11) In the table below, please indicate age range, gender, total number of subjects to be enrolled at MEE, and if multi-site, total number for the study:

	Age Range	Total Number at MEE	Total Number for the Study (if multi-site)
Adults (over 18)	18- no limit	140	140
Children (under 18)	NA	0	

12) Is a gender being excluded from this study? YES NO

IF YES, provide scientific justification:

Response:

13) Select all populations that may/will be enrolled (will not be excluded from the study) below. For some populations you may be asked to provide additional information.

- Pregnant Women
- Employees/Staff of MEEI or SERI-please specify:
- Healthy Controls

- Students/ Residents/ Fellows or other trainees
- Children
- Prisoner
- Non-English Speaking Subjects

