- 25) Will there be any out-of-pocket costs to subjects and/or expenses likely to be covered by their insurance for participating in the study? YES NO

IF YES, please specify in detail the costs to subjects and/or their insurance (e.g. co-pays):

RESPONSE: The study drug is provided by the pharmacy free of charge. The study medication supplies are charged to the study's cost center by the pharmacy.

- 26) If applicable, how will the cost of reasonably foreseeable medical care in the event of a research-related injury be covered (e.g., sponsor agreement, likely to be covered by insurance, grant, departmental funds)?

RESPONSE: This would be covered by patients' insurance.

RISK

Risk is the probability and magnitude of harm or discomfort anticipated as a result of participation in the research. Any risks of harm to subjects and/or anticipated discomfort(s) that are reasonably foreseeable, even if unlikely, and the safeguards in place to minimize these risks and discomfort(s) must be identified and discussed below. Risks of harm and discomfort may include: physical harm/discomfort, psychological harm/discomfort, legal harm/discomfort, social harm/discomfort, and economic harm.

- 27) Describe any risks of harm to subjects that are reasonably foreseeable, even if unlikely:

These are listed below:

1. amoxicillin/clavulanate arm:
From the FDA monograph
Gastrointestinal

Diarrhea, nausea, vomiting, indigestion, gastritis, stomatitis, glossitis, black “hairy” tongue, mucocutaneous candidiasis, enterocolitis, and hemorrhagic/pseudomembranous colitis. Onset of pseudomembranous colitis symptoms may occur during or after antibiotic treatment

Hypersensitivity Reactions

Skin rashes, pruritus, urticaria, angioedema, serum sickness–like reactions (urticaria or skin rash accompanied by arthritis, arthralgia, myalgia, and frequently fever), erythema multiforme (rarely Stevens-Johnson syndrome), acute generalized exanthematous pustulosis, and an occasional case of exfoliative dermatitis (including toxic epidermal necrolysis) have been reported. These reactions may be controlled with antihistamines and, if necessary, systemic corticosteroids. Whenever such reactions occur, the drug should be discontinued, unless the opinion of the physician dictates otherwise. Serious and occasional fatal hypersensitivity (anaphylactic) reactions can occur with oral penicillin.

Liver

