### **Statistical Analysis Plan**

The primary endpoint was the overall change in SNOT-22 scores from baseline to the final study visit. Secondary outcomes included the change in LK Endoscopic Score from the same time points, as well as rates of post-operative infection. Additional exploratory analyses included the effect of baseline clinical factors, including baseline sinus culture results, history of prior sinus surgery, comorbid asthma, and presence of nasal polyps.

The primary outcome and secondary outcome were analyzed using a repeated-measures analysis of variance (ANOVA) to assess for a group x time interaction on clinical scores. For the secondary analysis of the primary outcome, this model was modified to include baseline clinical covariates in a repeated-measures analysis of covariance (ANCOVA).

The achieved power for non-inferiority was calculated via the same methods as the prospective power analysis. Rather than an *a priori* estimate of standard deviation in scores, the achieved power was based on the actual number of randomized subjects and the actual pooled standard deviation of post-treatment SNOT-22 scores in the two groups. The non-inferiority margin was 9 units on the SNOT-22.

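### The plan sets a 9-unit non-inferiority margin but defines no analysis set, no interval against the margin and no analysis by study drug taken, so missed active drug could favour a not-worse result unseen

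*SAP*

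**What the plan says.** The protocol's aim is to show that antibiotics are not needed after sinus surgery (background response before question 4), and its answer to question 36 looks to a finding that patients without antibiotics do no worse. The SAP gives the yardstick: "The non-inferiority margin was 9 units on the SNOT-22".

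The SAP's analyses of SNOT-22 are a repeated-measures ANOVA testing a group-by-time interaction and a version of that model with baseline clinical covariates added. Non-inferiority appears only in connection with power: "The achieved power for non-inferiority was calculated via the same methods as the prospective power analysis". Randomised subjects are mentioned only there: "the achieved power was based on the actual number of randomized subjects". No intention-to-treat, per-protocol or as-treated set is named.

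On compliance, the answer to question 6b says the study's supervisor holds weekly meetings "on matters of enrollment, patient compliance, and monitoring of adverse events". It gives no measure, threshold or rate, and the SAP does not take compliance up.

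**The concern.** In a superiority trial, poor adherence works against the claim the sponsor hopes to make. In a non-inferiority trial it works for that claim. If the antibiotic helps, each active-arm subject who does not take it behaves more like a placebo subject, the observed difference moves toward zero, and the result falls inside the margin more easily.

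A reader of a favourable result would then need to know whether the arms were alike because the antibiotic adds little, or because many active-arm subjects went without it. No analysis in the SAP separates these. The ANOVA and ANCOVA contain only arm, time and baseline factors. Nor does the SAP say which subjects are analysed or how the result is compared with 9 units, so the starting point for such a check is itself undefined.

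**Working it through.** **Inputs from the documents**
- Margin: 9 SNOT-22 units (SAP, third paragraph).
- Total sample: 140 adults (protocol, question 11, table row "18- no limit 140 140").

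**Inputs assumed because the available text does not give them**
- 1:1 allocation, so 70 per arm.
- SD 15 to 25. The SAP gives no number and refers to "the actual pooled standard deviation of post-treatment SNOT-22 scores in the two groups".
- Non-inferiority claimed if the upper one-sided 97.5% limit for the placebo deficit is below 9.
- A true deficit under full adherence of exactly 9, so that any claim is false.
- A fraction L of the contrast lost, with effect proportional to drug taken and missed drug unrelated to prognosis.

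**The plan's own figure.** The prospective power calculation is not in the available text, so 140 can be neither confirmed nor refuted. Solving backwards with true difference 0:

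SD = 9 × √(70/2) / (z for alpha + z for power)

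At one-sided 2.5% and 80% power this is 53.24 / (1.960 + 0.842) = 19.0. At 90% power it is 16.4. With one-sided 5% the values are 21.4 and 18.2. All four fall within the assumed range.

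**Effect of lost contrast**

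SE = SD × √(2/70), which is 2.54, 3.38 and 4.23 for SD 15, 20 and 25.

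The expected deficit becomes 9 × (1 − L), so

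P(false claim) = Φ((9 − 1.96 × SE − 9 × (1 − L)) / SE) = Φ(9L/SE − 1.96)

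Example, SD 20 and L = 0.2: 9 × 0.2 / 3.38 = 0.53, and Φ(0.53 − 1.96) = Φ(−1.43) = 7.7%.

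| Contrast lost | Expected deficit | SD 15 | SD 20 | SD 25 |
|---|---|---|---|---|
| 0% | 9.0 | 2.5% | 2.5% | 2.5% |
| 10% | 8.1 | 5.4% | 4.5% | 4.0% |
| 20% | 7.2 | 10.6% | 7.7% | 6.3% |
| 30% | 6.3 | 18.5% | 12.3% | 9.3% |

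With a one-sided 5% rule and SD 19, the rates are 5.0%, 8.6%, 13.9% and 21.1%.

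Put another way, with 20% of the contrast lost, a full-adherence deficit of 9 / 0.8 = 11.25 units would appear as 9.

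**The case against.** The strongest reply is that the documents do not establish how the arms would converge. Much of this stands.

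- **Stopping for reactions.** A reader might take "the drug should be discontinued, unless the opinion of the physician dictates otherwise" (question 27) as a trial rule that will thin out the active arm. It sits in text attributed to the FDA monograph, within a list of risks, and carries no rate.
- **Infection at surgery.** A reader might infer open-label antibiotics in the placebo arm because one surgeon "does not prescribe antibiotics except when evidence of active infection was found during surgery". That is usual practice outside the trial. The eligibility criteria are not in the available text, so whether such patients are randomised cannot be judged.
- **Post-operative infection.** Infection is a secondary outcome, and question 32 describes an endoscopic check at one week. That infections are then treated is a fair inference, but no rule or rate is written. Nor does it follow that every such course pulls the difference to zero: the subject has already had symptoms that SNOT-22 can register, and later treatment is not the same as prophylaxis. If the question is a strategy of no routine prophylaxis with treatment if infected, those courses belong to the strategy.
- **As-randomised analysis.** A reader might say the SAP analyses non-inferiority strictly as randomised. It does not say so, and it specifies no non-inferiority test. The error rates above describe an assumed decision rule.
- **Bias in the per-protocol set.** Excluding everyone given a non-study antibiotic would remove placebo subjects whose infection was treated. Those are failures of withholding prophylaxis, so the exclusion could itself favour a not-worse result.

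These points narrow the concern and change the remedy. They do not remove it: missed active drug still dilutes a real effect, and nothing in the SAP would show it.

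**Conclusion.** The point holds in a limited form. The SAP sets a margin for a not-worse conclusion without defining the analysis set, without an interval against the margin, and without any analysis by study drug taken.

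The direction is certain if the antibiotic has a real effect; if it has none, missed drug does not bias the comparison. The size is not known. The rates for 10% and 20% lost contrast rest on assumed allocation, SD, alpha and loss fractions, and on a true deficit placed exactly at the margin. They are not estimates for this trial. The documents do not support a claim that adherence was poor, that open-label antibiotics were common, or that a false conclusion was reached.

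This should be corrected, because the change is small and bears directly on how a favourable result is read. Confidence is medium.

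**What to change.** 1. State that the primary comparison includes all randomised subjects by assigned arm, and set the confidence interval for the difference in SNOT-22 change against 9 units.
2. Add a supporting per-protocol analysis limited to subjects who took their assigned study drug to a threshold fixed before unblinding. Claim non-inferiority only if both analyses agree. A joint requirement cannot raise the false-claim rate above that of the randomised analysis alone.
3. Do not exclude subjects because they received antibiotics for post-operative infection; keep them in both sets.
4. Report by arm the numbers with incomplete study drug and with non-study antibiotics, with reason and timing.
5. The SAP is written in the past tense, and the protocol estimated completion in 06/2015 (question 4). If the data are already unblinded, label the added analysis post hoc and rely on whatever adherence and antibiotic data were recorded.

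The cost is SAP wording, one further model run and one table. It also depends on a usable record of study drug taken, which the protocol does not describe. The supporting set will be smaller with a wider interval, some selection remains because adherence is not randomised, and power for the joint claim is slightly lower. These changes concern analysis and reporting only, not who receives antibiotics.
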